14.1. Schedule of Assessments

Assessment	Screening ^a	Baseline	Titration		Treatment			Completion/ Early Termination	7 Day Follow-up	14 Day Follow- up	30 day Follow Up*
Study Week	Up to -4	0	2*	4 ^g	6 ^g	8 ^g	10*	12 ^g	13/14 ^g	14/15 ^g	16/17
Study Days	Up to -28	0	14 + 3	28 + 3	42 + 3	56 + 3	70 + 3	84 + 3	7 Days Post Last Dose +3	14 Days Post Last Dose +3	30 Days Post Last Dose +3
Study Visit Number	1	2	3	4	5	6	7	8	9	10	11
Informed Consent	Х										
Inclusion/ Exclusion	Х	Х									
Medical/Psychiatric/med ication History	х	х									
Randomization		Х									
Physical Exam/Vital Signs ^b	х	x		х	x	x		x	x	х	
ECG	Х	х		х	х	х		х	Х	х	
Laboratory tests (Hematology and Chemistry) ^c	x	x						x	x	Xc	
Urine Drug Screen	Х	Х						х			
Urine Pregnancy Test	Х	Х						х		Х	
DSM-5 Criteria for TS	Х										

Assessment	Screening ^a	B aseline	Titr	ation	Treatment			Completion/ Early Termination	7 Day Follow-up	14 Day Follow- up	30 day Follow Up*
Study Week	Up to -4	0	2*	4 ^g	6 ^g	8 ^g	10*	12 ^g	13/14 ^g	14/15 ^g	16/17
Study Days	Up to -28	0	14 + 3	28 + 3	42 + 3	56 + 3	70 + 3	84 + 3	7 Days Post Last Dose +3	14 Days Post Last Dose +3	30 Days Post Last Dose +3
Study Visit Number	1	2	3	4	5	6	7	8	9	10	11
Yale Global Tic Severity Scale	Х	х		х	х	x		х			
Clinical Global Impression - Tourette's Syndrome of Severity		x		x	x	x		x			
Clinical Global Impression - Tourette's Syndrome of Improvement				x	x	x		x			
Caregiver Global Impression of Change				х	х	х		x			
Columbia Suicide Severity Rating Scale	х	х	x	x	x	x	x	x	х	x	
Abnormal Involuntary Movement ^d		x		x	x	x		x			
Barnes Akathisia Rating Scale		х		х	x	x		x			
Swanson, Nolan, and Pelham Questionnaire		х		х	x	x		x			
Children's Yale-Brown Obsessive Compulsive Scale		x		x	x	x		x			

Assessment	Screening ^a	Baseline	Titration		Treatment			Completion/ Early Termination	7 Day Follow-up	14 Day Follow- up	30 day Follow Up*
Study Week	Up to -4	0	2*	4 ^g	6 ^g	8 ^g	10*	12 ^g	13/14 ^g	14/15 ^g	16/17
Study Days	Up to -28	0	14 + 3	28 + 3	42 + 3	56 + 3	70 + 3	84 + 3	7 Days Post Last Dose +3	14 Days Post Last Dose +3	30 Days Post Last Dose +3
Study Visit Number	1	2	3	4	5	6	7	8	9	10	11
Children's Depression Rating Scale - Revised		х		х	x	х		x			
Gilles de la Tourette Syndrome Quality of Life Scale		x		x	x	x		x			
Pediatric Anxiety Scale		Х		х	х	Х		х			
PK Blood Draws ^{e,h}				Х				х			
Adverse Events	х	х	х	х	х	х	х	x	х	х	X*
Concomitant Medications	x	х		х	x	x		x	x	х	
Dispense Study Drug		Х		х	х	Х		Xf			
Collect Unused Study Drug/Assess drug compliance				x	x	x		x	x		

Abbreviations: AE = adverse event; BP = blood pressure; ECG = electrocardiogram; HR = heart rate; PK = pharmacokinetic(s)

^a Informed consent must be performed prior to any screening procedures. All screening procedures are to occur after washout of any applicable medications. Rescreening is allowed after approval by the Medical Advisor.

^b Vital signs will include, pulse, BP, orthostatic BP (done 5 minutes after being supine and then 3 minutes after standing), height and weight.

^c Subjects should be in a fasting state (8 hours) for laboratory tests. HbA1c will be measured at the baseline and completion/early termination visits.

^d Every attempt should be made to perform this assessment at the same time at each visit.

^e At Week 4 Study dose should not be taken until after pre-dose blood draw at the site. PK draws should be pre-dose, between 0.5 and 1.5 hours after study drug administration, and between 2 and 4 hours after study drug administration. Both Week 4 and Week 12, visits should be scheduled for the morning. At Week 12, blood sample will be collected in the afternoon at the end of the visit.

f Study drug will be dispensed for dose down titration.

- * Weeks 2 and 10 will be telephone visits. If there are any abnormal findings, the subject will be brought to the site for full assessment. A telephone call will be made to the subject 30 days after the last visit to assess any adverse events that may have occurred.
- ^g Assessments for these visits may be completed in locations other than study clinic and/or safety and efficacy assessments required at these visits will be made available for remote administration due to restrictions as a consequence of the COVID-19 pandemic or other qualifying event.
- ^h If visits at Weeks 4 and 12 are completed in locations other than study clinic due to restrictions as a consequence of the COVID-19 pandemic or other qualifying event, then collection of labs for PK assessments are optional

14.2. Instruments

Exact copies of instruments and scoring algorithms are provided in additional documentation, literature references are stated in Section 13.

14.3. MAR multiple imputation methodology

The FCS method will be used to impute missing values for TTS of the YGTSS change values and will use age group at baseline, region, treatment arm, baseline YGTSS-TTS score and YGTSS-TTS scores at all visits up to week 12 to determine the scores (100 imputations will be created).

The SAS code for the imputation is as follows:

proc mi data=final out=mi1 seed=123 nimpute=100; class agegrp region arm ; var agegrp region arm base _4 _6 _8 _12; fcs regpmm; run;

14.4. MNAR jump to reference multiple imputation methodology

The monotone method will be used to impute missing values for TTS of the YGTSS change values and will use age group at baseline, region, and baseline TTS score to determine the scores (100 imputations will be created). Only placebo patients with complete data will be included in the imputation model.

The SAS code for the imputation is as follows:

```
proc mi data=final out=mi2 seed=123 nimpute=100;
class agegrp region arm;
monotone reg;
mnar model( _4 /modelobs=(arm='Placebo'));
mnar model( _6 /modelobs=( arm='Placebo'));
mnar model( _8 /modelobs=( arm='Placebo'));
```

```
mnar model( _12 /modelobs=( arm='Placebo'));
var agegrp region base _4 _6 _8 _12;
run:
```

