4.1.1. Primary Efficacy Estimand

The mean change from baseline in the Yale Global Tic Severity Scale – Total Tic Score to end of therapy are compared between ecopipam and placebo for patients aged 6 to less than 18 years eligible for the trial.

The primary estimand is defined as the following:

Treatment: 4-week titration period followed by 8-week treatment phase with ecopipam HCI doses or matching placebo.

Target Population: all children and adolescent patients with Tourette's syndrome who were randomized, received at least one dose of study drug, and had at least one post Baseline scoring of the YGTSS (mITT population).

Variable: the change in the Yale Global Tic Severity Scale (YGTSS) from baseline to Week 12.

Intercurrent events: For the intercurrent events, receiving prohibited concomitant medication, change in dosing of allowed concomitant medication, and no dosing adjustment with BMI change, the treatment policy strategy will be used for the primary analysis, meaning the observed data at Week 12 will be used for the change from baseline in YGTSS. For the intercurrent event of study treatment discontinuation due to lack of efficacy and treatment related adverse events, for subjects with no YGTSS at Week 12, the hypothetical strategy will be used, meaning the non-collected data of YGTSS at Week 12 will be multiple imputed using similar subjects (relevant demographic/baseline characteristics) from the placebo arm. The intercurrent event 'death prior to Week 12' will be handled using the 'while alive and on-treatment strategy' using the last observed YGTSS assessment for the analysis of Week 12.

Population-level summary: treatment difference between ecopipam and placebo treatment groups using MMRM model in mITT population after having applied the hypothetical strategy and the while-on-treatment strategy, respectively, to the non-collected / non-observed Week 12 YGTSS assessments specified above.

The primary efficacy analysis approach is in line with the primary estimand. Potential confounders will be identified and sensitivity and/or supplementary analysis may be used to deal with missing data and assess the robustness of conclusions.

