8.1.2.1. Sensitivity analyses for missing data

Sensitivity analyses for missing data includes MAR predictive mean matching multiple imputation method, MNAR jump to reference multiple imputation method, and MNAR tipping point analysis. Details for the sensitivity analysis for missing data are given below:

1) MAR predictive mean matching multiple imputation method

All missing data will be imputed for patients missing data at week 12 using the predictive mean matching multiple imputation method (Heitjan and Little 1991, Schenker and Taylor 1996) for a MAR data assumption using fully conditional specification (FCS) method. The imputation model will include age group at baseline, region, treatment arm, baseline YGTSS-TTS, and YGTSS-TTS at all visits up to week 12 where the YGTSS is scheduled to be collected. This imputation will be performed using the SAS MI procedure with fcs specification. The resulting complete, imputed datasets will each be analyzed using the same model as the primary analysis model, and the resulting statistics combined using methodology provided by Rubin (1987) and Little and Rubin (2002). The SAS code for the multiple imputation methodology is detailed in the Appendix (Section 14.3).

2) MNAR jump to reference multiple imputation method

Data will be imputed for patients missing data at week 12 using similar predictive mean matching multiple imputation method. Under a MNAR data assumption, patients will have their missing data at week 12 imputed as if they behaved like placebo treated patients after dropout. Only placebo patients with complete data will be included in the imputation model. The imputation models will include age group at baseline, region, baseline YGTSS-TTS score, and YGTSS-TTS scores at all visits up to week 12 where the YGTSS is scheduled to be collected. After obtaining complete data sets, the complete data sets will be used in the analysis. The resulting complete, imputed datasets will each be analyzed using the same model as the primary analysis model, and the resulting statistics combined using methodology provided by Rubin (1987) and Little and Rubin (2002). The SAS code for the multiple imputation methodology is detailed in the Appendix (Section 14.4).

3) Tipping point analysis:

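### The jump-to-reference sensitivity analysis is specified in three conflicting ways, and its code is a copy-reference method that on average carries part of any drug benefit forward

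*SAP*

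**What the plan says.** SAP 8.1.2.1 lists three missing-data sensitivity analyses for the primary endpoint. The second is named jump to reference. Its stated aim is that "patients will have their missing data at week 12 imputed as if they behaved like placebo treated patients after dropout". Three descriptions of how to do this follow.

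| Place | Method | Predictors |
|---|---|---|
| SAP 8.1.2.1 | "using similar predictive mean matching multiple imputation method" | "The imputation models will include age group at baseline, region, baseline YGTSS-TTS score, and YGTSS-TTS scores at all visits up to week 12" |
| SAP 14.4, text | monotone method | "age group at baseline, region, and baseline TTS score to determine the scores" |
| SAP 14.4, code | monotone linear regression | "var agegrp region base _4 _6 _8 _12" |

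The code fits each visit's model in placebo subjects, for example "mnar model( _12 /modelobs=( arm='Placebo". Both prose versions also limit the model to placebo subjects with complete data, whereas the code limits it by arm only.

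The estimand in SAP 4.1.1 bears on this too. After discontinuation for lack of efficacy or treatment-related adverse events, a missing Week 12 score "will be multiple imputed using similar subjects (relevant demographic/baseline characteristics) from the placebo arm".

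**The concern.** The three descriptions differ in method, in predictors or in both, so a programmer cannot follow all of them. The label does not settle the matter, because the code does not do what the label says.

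In jump to reference, an average dropout moves to the placebo mean after leaving treatment. The subject's own history enters only as a residual from the own-arm mean. The code instead takes placebo regression coefficients and feeds in the ecopipam subject's raw earlier scores. If those scores are better than placebo because of the drug, the prediction treats the subject as a placebo patient who happened to be doing well, and part of the benefit persists to Week 12. That is copy-reference. The version in 8.1.2.1 has the same feature.

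Membership of the mITT set requires a post-baseline YGTSS (SAP 5.3), so every ecopipam dropout analysed brings at least one such score. This is also the only placebo-based imputation for which the SAP gives code. A reader who trusts the label would think the primary result had passed a stricter test than it had.

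**Working it through.** **1. The plan's own figures.** Inputs from SAP 3.5: difference 3, SD 6.1, alpha 0.05 (two-sided per SAP section 11), 10% dropout, 75 per arm.

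- n per arm for 80% power = 2 × (1.960 + 0.842)² × 6.1² / 3² = 64.9, so 65. Inflated: 65 / 0.9 = 72.2, so 73.
- With 75 × 0.9 = 67.5 per arm, power is 81.5%.

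The stated power of more than 80% is reproduced, so the 3 points and 10% are used below.

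**2. Share of the effect kept.** Write β for the placebo coefficients of the Week 12 score on the observed post-baseline scores, given baseline. Write δ for the drug effect at each visit. For a dropout with the average drug response:

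- True jump to reference: the residual from the own-arm mean averages zero, so the share kept is 0.
- Baseline-only predictors (14.4 text): no post-baseline score enters, so the share kept is 0.
- Code: share kept = Σ βⱼδⱼ / δ₁₂. Predictive mean matching on the same predictors (8.1.2.1) aims at the same conditional mean.

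The documents give no correlation between visits. The assumption here is a marginal correlation ρ of 0.5 to 0.8, equal variances and an effect constant over visits. With k post-baseline scores observed:

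- Compound symmetry (CS), baseline also a predictor: share = kρ / (1 + kρ).
- AR(1) per scheduled visit: share = ρ^m, where m is the number of visits missed up to and including Week 12.

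| Last score | CS 0.5 | CS 0.8 | AR(1) 0.5 | AR(1) 0.7 | AR(1) 0.8 |
|---|---|---|---|---|---|
| Week 4 (k=1, m=3) | 0.33 | 0.44 | 0.125 | 0.34 | 0.51 |
| Week 6 (k=2, m=2) | 0.50 | 0.62 | 0.25 | 0.49 | 0.64 |
| Week 8 (k=3, m=1) | 0.60 | 0.71 | 0.50 | 0.70 | 0.80 |

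The ranges are therefore about 13-51%, 25-64% and 50-80%. Simulating the sequential placebo regression with 100,000 subjects per arm gave 0.35, 0.50 and 0.69 for AR(1) 0.7, and 0.51, 0.64 and 0.79 for AR(1) 0.8.

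**3. Two checks on the assumptions.**

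- *Correlation.* Study PSY302 (Protocol 5.2.2.1) reports a baseline SD of 6.7 before placebo, and SDs of change on placebo of 4.7 (Day 16) and 5.8 (Day 30). With equal SDs, ρ = 1 − SD²change / (2 × 6.7²), which gives 0.75 and 0.63. Under CS the shares are 38-43%, 56-60% and 65-69%, inside the ranges above. This is a rough anchor from a crossover study with shorter treatment.
- *Timing.* Most weight bands reach target dose only in Week 4 (SAP 3.7). If 50%, 75% and 100% of the effect were present at Weeks 4, 6 and 8 (assumed), AR(1) 0.7 gives 0.17, 0.37 and 0.70 instead of 0.34, 0.49 and 0.70.

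**4. Effect on the trial estimate.** At 10% ecopipam dropout:

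- True jump to reference removes 0.10 × 3 = 0.30, leaving 2.70.
- The code removes 0.30 × (1 − share). For share 0.125 this is 0.26, leaving 2.74. For share 0.80 it is 0.06, leaving 2.94.
- The gap is 0.04 to 0.24 points. The planned standard error is 6.1 × √(2/67.5) = 1.05, so the gap is at most 0.24 / 1.05 = 0.23 of a standard error.

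**The case against.** The case on the other side limits this point in several ways.

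- *Use of own scores was planned.* Section 8.1.2.1 openly includes all visit scores, and true jump to reference also uses a subject's own scores. This stands. Conditioning on them is not the fault. The fault is entering them raw, without taking them as deviations from the own-arm mean.
- *The percentages are assumed.* A reader might infer that the code is known to keep a third to four-fifths of the effect. The documents do not support a fixed figure: no correlation is given, AR(1) at 0.5 keeps as little as 12.5% after Week 4, and an effect still building lowers the share further.
- *The inconsistency is not the cause.* A reader might infer that the three-way mismatch produces the retention. It does not, since the 14.4 text on its own would keep none. The mismatch and the unadjusted scores are separate defects.
- *The estimand does not settle it.* One might read SAP 4.1.1 as requiring baseline-only imputation here. It covers only discontinuation for lack of efficacy or treatment-related adverse events with no Week 12 score, not this all-cause analysis.
- *The direction is an average.* An ecopipam dropout scoring worse than the placebo average at the last visit gets a worse imputed value from the code than from baseline-only predictors.
- *Robustness does not rest on this alone.* The tipping-point analysis in SAP 8.1.2.1 and 14.5 penalises ecopipam dropouts and rewards placebo dropouts by up to 10 points or more. It remains a further check, though it does not make the label on this analysis correct.

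**Conclusion.** The point holds as a specification error in one sensitivity analysis. The three descriptions conflict, and the coded method is copy-reference under a jump-to-reference label. On average the code favours ecopipam relative to the label, if the drug improves scores and visits are positively correlated.

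The size is modest: 0.04 to 0.24 points of a 3-point effect. This rests on 10% dropout in the ecopipam arm, correlation 0.5 to 0.8, a constant effect, and dropouts who had the average drug response before leaving.

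A reader might go further and conclude that the primary result is compromised. The documents do not support that. SAP 8.1.2 makes the primary analysis an MMRM on observed data, so this code touches neither the primary test nor its type I error.

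**What to change.** Before unblinding:

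1. Make 8.1.2.1, the 14.4 text and the 14.4 code agree on method, predictors and which placebo subjects inform the model.
2. Either implement true jump to reference (placebo mean profile after dropout, with the subject's residual taken from the own-arm mean before dropout), or keep the present code and call it copy-reference.
3. Impute intermittent gaps first. The code in 14.4 relies on a monotone pattern but includes no step to create one, whereas 14.5 at least addresses this.

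Restricting the model to age group, region and baseline should not be offered as an equivalent fix. It ignores the observed poor response of subjects who leave for lack of efficacy, and could make the result more favourable to ecopipam.

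The cost is SAP text and a small amount of code, with no change to data collection, sample size or the primary analysis. Under true jump to reference the sensitivity estimate would be expected to be slightly less favourable. Under relabelling alone it would not change.

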14.5. Tipping Point Analysis

Let delta1 and delta2 be the penalty to ecopipam group and reward for placebo group, respectively. Delta1 and delta2 = 1 to 10 (or estimated treatment effect from primary analysis if it is larger than 10) in step of 1. General steps for this analysis includes:

Step 1:

For each combination of (delta1, delta2), 100 imputations will be created.

In order to induce monotonicity, an imputation model will first be used to impute missing values for TTS of the YGTSS week 4 change values and will use age group at baseline, treatment arm, and baseline TTS score to determine the scores.

The SAS code for the imputation is as follows:

```
proc mi data=final out=mi seed=666 nimpute=100;
class agegrp region1 arm;
var agegrp region1 arm base _4;
monotone regpmm; run;
```

* Create delta1, delta2 in the dataset;

```
data mitv1;
set mi;
do i=1 to 10;
do j=1 to 10;
delta1=i; delta2=j; output;
end;
end;
run;
```

```
data mitv1;
set mitv1;
if firstdrp=4 and missdm in ("MNAR') and index(arm, 'ecopipam') then _&cv=_&cv+delta1;
else if firstdrp=4 and missdm in ("MNAR') and arm='Placebo' then _&cv=_&cv-delta2;
run;
```

For each visit after week 4: %macro tippimp (cv, pv, pvs, seed);

```
proc mi data=mitv&pv out=mitv¤tv seed=&seed nimpute=1;
class agegrp region1 arm;
var agegrp region1 arm base _&cv &pvs;
monotone regpmm;
by _Imputation_ &delta1 &delta2; run;
data mitv&cv;
```

```
if firstdrp=&cv and missdm in ("MNAR') and index(arm, 'ecopipam') then _&cv=_&cv+delta1;
else if firstdrp=&cv and missdm in ("MNAR') and arm='Placebo' then _&cv=_&cv-delta2;
run;
%mend;
```

```
% tippimp (6, 4, _4 , 2626);
% tippimp (8, 6, 4, %str(_4 _6), 2828);
% tippimp (12, 8, 6, 4 %str(_4 _6 _8), 2929);
```

Step 2

The resultant complete data sets will be analyzed using the same model as the primary analysis. The SAS code is as follows:

proc sort data=mitv12; by delta1 delta2 _imputation_ descending arm avisitn; run;

proc mixed data=all order=data; by delta1 delta2 _imputation_; class usubjid arm avisitn agegrp region1; model chg=arm avisitn arm*avisitn agegrp region1 base / ddfm=sat; repeated avisitn / type=un subject=usubjid; Ismeans arm*avisitn / diff cl; ods output diffs=diff(where=(avisitn=_avisitn) Ismeans=Ism; run;

```
Step 3
```

The results from the imputed data analysis will be combined using PROC MIANALYZE which will provide the LS mean and standard error of the LS mean for each treatment group at each visit as well as the LS mean difference, 95% CI and resultant p-value between the ecopipam and placebo groups at each visit. The SAS code is as follows:

proc sort data=diff; by delta1 delta2 avisitn arm; run; proc sort data=lsm; by delta1 delta2 avisitn arm; run; proc mianalyze data=diff; by delta1 delta2 avisitn arm; modeleffects estimate; stderr stderr; ods output ParameterEstimates=estdiff; run; proc mianalyze data=lsm; by delta1 delta2 avisitn arm; modeleffects estimate; stderr stderr;

ods output ParameterEstimates=estIsm; run;

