In the event that statistical significance in favor of ecopipam is determined from the primary analysis, subjects in the ecopipam group with a missing YGTSS-TTS score (change from baseline) will be assigned successively more extreme values, whilst subjects in the placebo group with a missing YGTSS-TSS score (change from baseline) will be assigned successively less extreme values, to find the point at which statistical significance is lost (i.e. the 2-sided P-value becomes greater than 0.05)

Details for tipping point analysis are described below:

- a. For patients that completed the study, intermittent missing data are considered as MAR and will be imputed by predictive mean matching multiple imputation method (Heitjan and Little 1991, Schenker and Taylor 1996). The imputation model will include age group at baseline, region, treatment arm, baseline TTS score, and TTS scores at all visits up to the imputed visit where the TTS is scheduled to be collected.
- b. For patients who discontinued due to any reason, all missing data will be imputed using the same predictive mean matching multiple imputation method. The imputed values will be adjusted under MNAR assumption:
 - Patients randomized to ecopipam: the first missing value after patients dropout will be analyzed assuming the unobserved outcome is on average worsened by ō1 (where ō1 = 1 to 10 or estimated treatment effect, whichever is higher, in step of 1) compared to the patients who have no missing value;
 - Patients treated by placebo: the first missing value after patients dropout will be analyzed assuming the unobserved outcome is on average better by 52 (where 52 = 1 to 10 or estimated treatment effect, whichever is higher, in step of 1) compared to the patients who have no missing value;

The penalty or reward will not be applied to the values from later time points as these values are penalized or rewarded through condition on previous time points. For each combination of ($\overline{0}1$, $\overline{0}2$), 100 imputed datasets will be obtained.

c. The resulting complete, imputed datasets will each be analyzed using the same model as the primary analysis model, and the resulting statistics combined using methodology provided by Rubin (1987) and Little and Rubin (2002).

The complete multiple imputation methodology, along with SAS code, is detailed in Appendix (Section 14.5).

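### The tipping-point program printed in SAP 14.5 does not carry out the imputation that SAP 8.1.2.1 specifies

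*SAP*

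**What the plan says.** SAP 8.1.2.1, item 3, sets out the tipping-point method. The imputation model contains age group, region, arm, baseline and "TTS scores at all visits up to the imputed visit where the TTS is scheduled to be collected". Dropouts are imputed by the same predictive mean matching. A penalty (ecopipam) or reward (placebo) of 1 to 10 points is added at the first missed visit only, and later values are to feel it because they are conditioned on the earlier ones. The analysis is run if the primary result is significant. Item 3 points to 14.5 for the full method and its code.

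In 14.5, Step 1, the macro is defined as "macro tippimp (cv, pv, pvs, seed", that is, with four parameters. Inside it, a MONOTONE REGPMM step uses "var agegrp region1 arm base _&cv &pvs;". The three calls begin:

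- Week 6: "tippimp (6, 4, _4 , 2626"
- Week 8: "tippimp (8, 6, 4, %str(_4 _6), 2828"
- Week 12: "tippimp (12, 8, 6, 4 %str(_4 _6 _8), 2929"

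The Week 4 shift, which comes before the macro, is also written on `_&cv`. By contrast, the code in 14.3 and 14.4 lists the visits in time order. For the placebo-based analysis, 14.4 states: "The monotone method will be used to impute missing values". It applies this directly to the raw data.

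**The concern.** Conditioning on earlier visits does two jobs in 8.1.2.1. It makes a dropout's imputed Week 12 score depend on that child's own course, and it is the only route by which a shift at Week 4, 6 or 8 reaches the Week 12 endpoint. A program without it does not test what the text says it tests. Because the analysis is triggered by a significant primary result, a fault not found beforehand would be repaired after unblinding, by choices that the plan does not fix.

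**Working it through.** **1. Predictors implied by the VAR order.** With MONOTONE and no explicit covariate list, each variable is predicted from those listed before it, and a missing value must be followed only by missing values. This is standard SAS behaviour, not something the SAP states. Binding the arguments by position gives:

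| Call | Arguments | cv | pvs | seed | Left over | Resulting VAR list |
|---|---|---|---|---|---|---|
| Week 6 | 4 | 6 | `_4` | 2626 | none | `... arm base _6 _4` |
| Week 8 | 5 | 8 | `4` | `%str(_4 _6)` | 2828 | `... arm base _8 4` |
| Week 12 | 5 | 12 | `6` | `4 %str(_4 _6 _8)` | 2929 | `... arm base _12 6` |

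The Week 6 call is aligned; there the order alone is at fault. `_6` can draw only on age group, region, arm and baseline. A child with Week 4 filled and Week 6 missing is missing then present in that order, so the pattern is not monotone and the step should stop. The Week 8 and Week 12 calls fail earlier, on the surplus argument.

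**2. Other breaks in the same code.**

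- `_&cv` is used before the macro, where `cv` has no value.
- The first call reads `mitv4`, but the step before it creates `mitv1`.
- `&currentv`, `&delta1` and `&delta2` are never defined.
- There is no sort before the BY step.
- Step 2 sorts `mitv12` but analyses `all`.

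The missing SET statement and the mismatched quotes may be PDF losses, and nothing here rests on them.

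**3. What a baseline-only repair would do.** The SAP gives no figure for this analysis. Its design inputs (SAP 3.5: 75 per arm, difference 3, SD 6.1, 10% dropout) reproduce: 2 × (1.96 + 0.842)² × 6.1² / 3² = 64.9, so 65 evaluable per arm; 65 / 0.9 = 72.2, so 73, within the planned 75.

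The illustration assumes nine dropouts per arm (12%), three each first missing at Weeks 6, 8 and 12, and delta1 = delta2 = 10. Let D be the movement in the Week 12 arm difference among the six per arm first missing at Week 6 or 8. Then:

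overall movement = (3/75) × (10 + 10) + (6/75) × D = 0.8 + 0.08 × D

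- Baseline-only predictors: D = 0, so the movement is 0.8. All of it comes from children first missing at Week 12. A simulation with separate random draws for the shifted and unshifted runs gave 0.6 to 0.7, and D between -0.3 and 0.2. With shared draws it returns exactly 0.8 and 0.
- Earlier visits as predictors: predictive mean matching with five donors and assumed AR(1) visit correlations of 0.5, 0.7 and 0.85 gave D of about 5.5, 10.3 and 14.2, with Monte Carlo error of roughly half a point. The formula then gives 0.8 + 0.44 = 1.24, 0.8 + 0.82 = 1.62 and 0.8 + 1.14 = 1.94, matching the simulated 1.2, 1.6 and 1.9.

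**4. Section 14.4.** MONOTONE stops if any child has a gap followed by an observed visit. With 150 × 0.9 = 135 completers and three intermediate YGTSS visits each, there are 405 chances of a gap. If visits are missed independently with probability p (not given in the documents), the chance of no gap is (1 - p)^405: 1.7% at p = 1% and 0.03% at p = 2%.

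**The case against.** The best reply is that 8.1.2.1 states the method clearly, that 14.5 presents its code as general steps, and that a program that stops misleads nobody: validation would catch it, and a programmer would reorder the list to match 8.1.2.1, 14.3 and 14.4. Much of this stands. No biased estimate comes from the code as printed. This is one of three missing-data sensitivity analyses.

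It does not dispose of the point. Section 8.1.2.1 names 14.5 as the full methodology with code, so two parts of one pre-specified analysis disagree. Neither the variable order nor the argument count is plausibly an extraction fault.

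Three stronger readings are tempting, and the documents do not support them:

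- A reader might infer that the plan carries a known bias. A simulation in which ecopipam dropout follows poor scores and placebo dropout is random puts the unshifted estimate at -3.18 to -3.25 with baseline-only predictors, against -2.97 to -3.02 with earlier visits. That needs both a hypothetical repair and a dropout mechanism that the documents do not give. It also used regression imputation and a Week 12 ANCOVA, not the SAP's matching and MMRM.
- A reader might infer that both MNAR programs cannot run. Section 14.4 fails only if an intermittent gap occurs.
- A reader might take the monotonicity step in 14.5 as an admission that 14.4 lacks one. That step fills Week 4 values only and says nothing about 14.4.

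**Conclusion.** The concern holds: the program in SAP 14.5 contradicts SAP 8.1.2.1 and should be corrected before unblinding. The faults can be read directly from the printed code, given standard MONOTONE and macro behaviour; the most likely outcome is a visible error.

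The harm to interpretation is conditional. Under a repair with baseline-only predictors, the stress at the largest shifts would be understated by about 0.4 to 1.1 points at Week 12 (0.08 × D). The primary result would then look more robust than 8.1.2.1 intends. That range is illustrative and depends on the assumed correlations, dropout count and timing.

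The 14.4 weakness is separate: conditional on a gap, but likely to bite. SAP 8.1.2.1 itself provides for intermittent missing data in completers, and 8.3 plans a table of data missing because of COVID-19.

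**What to change.** In SAP 14.5:

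- Write the later-visit list as `var agegrp region1 arm base &pvs _&cv;`.
- Call `%tippimp(6, 4, _4, 2626)`, `%tippimp(8, 6, _4 _6, 2828)` and `%tippimp(12, 8, _4 _6 _8, 2929)`.
- Apply the Week 4 shift to `_4`.
- Name the data sets consistently: Week 4 output `mitv4`, then `out=mitv&cv` and `set mitv&cv`, with the Step 2 input built from `mitv12`.
- Sort by `_Imputation_ delta1 delta2` and use these as plain variables in the BY statement.

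In SAP 14.4, first fill intermittent gaps under MAR with arm in the model, then apply the placebo-based step to visits after dropout.

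Dry-run both programs on blinded data before unblinding. Include a check that, for a child first missing at Week 6, the imputed Week 12 value responds to the shift.

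The cost is an appendix correction and the dry run. Data collection, design and the primary analysis do not change.
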